3.3. Dose-Limiting Toxicity Definition

Severity of AEs will be graded according to CTCAE v.4.03. For the purpose of the Phase 1b lead-in, any of the following AEs occurring during the DLT observation period (the first 2 cycles of treatment [8 weeks] for combinations A to D, and the first treatment cycle [4 weeks] for combination F) which are attributable to one or more of the investigational products in the combination will be classified as DLTs:

Hematologic:

- Grade 4 neutropenia (absolute neutrophil count [ANC] <500/mm³ or <0.5 x 10⁹/L) lasting >7 days;
- Febrile neutropenia, defined as ANC <1000/mm³ with a single temperature of >38.3 degrees C (>101 degrees F) or a sustained temperature of ≥38 degrees C (100.4 degrees F) for more than 1 hour;
- Neutropenic infection (ANC <1,000/mm³ or <1.0 x 10⁹/L, and Grade >3 infection);
- Grade ≥3 thrombocytopenia (platelet count <50,000 - 25,000/mm³ or <50.0 – 25.0 x 10⁹/L) with bleeding;
- Grade 4 thrombocytopenia (platelet count <25,000/mm³ or <25.0 x 10⁹/L);
- Grade 4 anemia.

Non-Hematologic (Non-Laboratory):

- Any Grade ≥3 toxicity, except for any of the following:
 - Transient (≤24 hours) Grade 3 fatigue, local reactions, or headache that resolves to Grade ≤1;

- Grade 3-4 nausea and vomiting controlled by optimal medical therapy within 72 hours;
- Grade 3 hypertension controlled by medical therapy;
- Grade 3 diarrhea that improves to Grade ≤ 2 within 72 hrs after medical management has been initiated;
- Grade 3 skin toxicity that resolves to Grade ≤ 1 in less than 7 days after medical management (eg, immunosuppressant treatment) has been initiated;
- Any Grade ≥ 3 amylase or lipase abnormality that is not associated with symptoms or clinical manifestations of pancreatitis;
- Grade 3 endocrinopathies controlled with medical therapy;
- Tumors flare phenomenon defined as local pain, irritation, or rash localized at sites of known or suspected tumor.
- Grade 4 CRS or Grade 3 CRS lasting >24 hours despite optimal treatment.

Important for Combination F: CMP-001 activates pDCs through agonism of TLR9. Upon activation by CMP-001, pDCs will induce large amounts of IFN α and Th1-promoting cytokines. Therefore, it is expected that toxicities associated with CMP-001 dosing may resemble interferon-related toxicities and symptoms associated with cytokine release, such as fever, flu-like symptoms, tachypnea, headache, tachycardia, hypotension, rash, and hypoxia which may present hours after CMP-001 injection. Therefore, AEs such as headache, fever, flu-like symptoms and/or hypotension that are \leq Grade 3 AND resolved to \leq Grade 1 within 24 hours with standard supportive care will not be considered as DLTs.

- Non-hematologic Grade ≥ 3 laboratory abnormality if medical intervention is required to treat the patient or the abnormality leads to hospitalization.
- Single laboratory values out of normal range that are unlikely related to trial treatment according to the Investigator, do not have any clinical correlate, and resolve to Grade ≤ 1 within 7 days with adequate medical management are not to be considered DLTs;
- ALT or AST $>3 \times$ upper limit of normal (ULN) (if normal at baseline) or $>3 \times$ ULN and doubling the baseline (if $>$ ULN at baseline) associated with bilirubin $>2 \times$ ULN.

Non-Adherence to Treatment Schedule:

- Delay of ≥ 3 weeks in receiving the next scheduled administration due to persisting treatment-related toxicities;

- Failure to receive at least 75% of the planned doses each of the investigational products during the DLT observation period due to treatment-related toxicities.

In the absence of associated clinical abnormalities, abnormal laboratory tests should be repeated to confirm relevance.

While the rules for adjudicating DLTs in the context of the dose determination phase (Phase 1b) are specified above, an AE not listed above, or an AE meeting the DLT criteria above but occurring outside of the DLT observation period may be defined as a DLT after consultation between Sponsor and Investigator, based on the emerging safety profile.

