5.3.7.3.4. Management of Injection Site-Reactions

If a patient develops inflammation at the injection site, this may be managed using cold compresses and/or acetaminophen or NSAIDs.

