9.1.3. Evaluable for DLT Analysis Set

This is the primary analysis set for the Phase 1 lead-in parts for all Combinations and includes all enrolled patients in Phase 1b who are eligible for the study, receive at least 1 dose of study treatment, and either experience DLT during the DLT observation period, or complete the DLT observation period. For Combinations A, B, C, and D, the DLT observation period is the first 2 cycles (8 weeks) of treatment. For Combination F, the DLT observation period will be 4 weeks including the first two weekly SC injections and the subsequent two weekly IT administrations.

Patients without DLTs who withdraw from study treatment before receiving at least 75% of the prescribed doses for all investigational products in the combination for reasons other than treatment-related toxicity (eg, missed appointments or development of rapidly progressing disease) are not evaluable for DLT.

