Appendix 4. CMP-001 Administration

Tumor Selection

It is recommended that the tumors selected at baseline for CMP-001 intratumoral injection be at least 1 cm in diameter and may be cutaneous, subcutaneous, and/or nodal or visceral tumors that are visible, palpable, or detectable by appropriate imagining guidance. The lesion must be safe to inject. The assessment for safety should consider following aspects:

- Proximity to major blood vessels: lesions in the vicinity of large vessels with a risk of vessel blow out (eg, the common, internal or external carotid arteries or their branches), or other situations with a risk of vascular catastrophe such as tumor-encased large vessels should be excluded. Special caution should be taken in patients with neck lesions that have been re-irradiated, especially if the second course of radiation was given at radical doses with curative intent and in whom the disease is ulcerated and/or connects to a skin or mucosal surface. Also, patients with tumor lesions with macroscopic intravascular tumor invasion (eg, liver lesions with tumor infiltration into the main portal vein, hepatic vein or vena cava) should not receive intratumoral therapy.¹⁰³
- Potential for airway obstruction: lesions in close proximity to airway and potential to obstruct airway with slight increase in size should be avoided eg, hypopharynx, larynx, trachea.

The most preferred of these to be selected for injection is the most aggressively progressing tumor in the judgment of the Investigator. The tumor selected for injection does not need to be the largest lesion.

CMP-001 can be injected into target or non-target lesions, although target lesions are preferred. Preferably single large lesions should be injected with the entire dose of 10 mg. If the total dose of CMP-001 is to be split across lesions, a minimum of approximately 5 mg should be injected into each lesion. The same tumor(s) should be injected each week during therapy, if possible, except as outlined below to involuting tumors. If the full volume cannot be administered into the tumor, peritumoral injection of any remaining volume is acceptable.

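### The uncapped tumour-flare exemption in Section 3.3 takes Grade ≥3 pain or irritation at a CMP-001-injected lesion out of the Combination F DLT count, bypassing the 24-hour limit on local reactions

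*Protocol*

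**What the plan says.** Protocol Section 3.3 treats any attributable non-haematologic, non-laboratory toxicity of Grade 3 or higher as a DLT, subject to a list of exemptions. The list is worded so that meeting any single item is enough. Two items matter here:

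- Local reactions are exempt only as "Transient (≤24 hours) Grade 3 fatigue, local reactions, or headache that resolves to Grade ≤1".
- The tumour-flare item reads "Tumors flare phenomenon defined as local pain, irritation, or rash localized at sites of known or suspected tumor". It states no grade, duration or resolution condition.

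A separate Combination F paragraph in Section 3.3 exempts expected cytokine-type events such as headache, fever, flu-like symptoms and hypotension. It does so only up to Grade 3 and only if they settle to Grade ≤1 within 24 hours on supportive care. It does not mention injection-site reactions.

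For Combination F, Section 9.1.3 says "the DLT observation period will be 4 weeks including the first two weekly SC injections and the subsequent two weekly IT administrations". Appendix 4 says "CMP-001 can be injected into target or non-target lesions, although target lesions are preferred". Section 5.3.7.3.4 treats injection-site reactions as a topic of their own: "If a patient develops inflammation at the injection site, this may be managed using cold compresses and/or acetaminophen or NSAIDs". Nothing there refers back to either exemption.

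**The concern.** A tumour-flare exemption makes sense for intravenous agents, where local pain at a tumour site is hard to separate from an immune effect on the tumour. In Combination F the tumour is also the injection site. Pain caused by the injected drug or by the procedure therefore meets the flare definition simply because of where it occurs. The limit that the protocol sets on local reactions then does no work at the one place where local reactions to CMP-001 are most expected after intratumoral dosing.

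DLT is the Phase 1b primary endpoint (Section 2.2). Under Sections 3.2.5 and 9.2.3, a count of 0–1, 2, or 3 or more DLTs in six patients decides whether a cohort expands, adds six patients or stops. An exemption that can remove drug-caused local toxicity of any grade therefore acts directly on that decision.

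**Working it through.** **1. The two exemptions side by side, applied to an injected lesion**

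| | Local reaction | Tumour flare |
|---|---|---|
| Grade limit | Grade 3 only | none |
| Duration | ≤24 hours | none |
| Resolution | to Grade ≤1 | none |
| Defined by | type of reaction | symptom (pain, irritation, rash) and tumour site |

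Take attributable Grade 3 pain at an injected lesion lasting three days. It fails the local-reaction exemption on duration. It meets the flare definition because the lesion is known tumour. One exemption suffices, so the event is not a DLT. The same holds at Grade 4.

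**2. Whether dosing falls inside the window.** Table 20 gives SC doses at C1D1 and C1D8 and intratumoral doses at C1D15 and C1D22. Both intratumoral doses lie within the 28-day window. SC doses away from tumour cannot meet the flare definition, so they remain under the local-reaction limit.

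**3. Whether other parts of Section 3.3 catch the event**

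- *Delay.* A delay of three or more "weeks in receiving the next scheduled administration due to persisting treatment-related toxicities" is a DLT. In nominal days for CMP-001, after a reaction at C1D15 the next dose is due on Day 22, and 22 + 21 = Day 43. After a reaction at C1D22 the next dose is due on Day 29, and 29 + 21 = Day 50. Either way the rule is met only 28 days after the injection (43 − 15 = 50 − 22 = 28).
- *Missed doses.* The rule is "Failure to receive at least 75% of the planned doses each of the investigational products during the DLT observation period". If only C1D22 is missed, 3 of 4 CMP-001 doses = 75% have been given, so the rule is not triggered.
- *Consultation.* An event that is not listed, or that falls outside the window, "may be defined as a DLT after consultation between Sponsor and Investigator, based on the emerging safety profile". This is discretionary. Flare is listed, as an exemption, so whether the clause reaches it is unclear.
- *Rash.* Grade 3 skin toxicity resolving to Grade ≤1 in under 7 days of management is exempt anyway. Swelling and induration are not in the flare definition.

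What remains is mainly Grade ≥3 pain or irritation at an injected lesion lasting from just over 24 hours to about four weeks.

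**4. The decision rule the count feeds.** P(expand) = P(X₆ ≤ 1) + P(X₆ = 2) × P(Y₆ ≤ 1), where X₆ and Y₆ are binomial DLT counts in the first and second six patients.

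- True rate 10%: 0.8857 + 0.0984 × 0.8857 = 0.973 (Table 29: 0.97).
- True rate 20%: 0.6554 + 0.2458 × 0.6554 = 0.816 (Table 29: 0.82).

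The other entries of Table 29 also reproduce.

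**5. Illustration only.** Let q be the rate of other DLTs and r the rate of the exempted events, assumed independent. The combined rate is 1 − (1 − q)(1 − r). The protocol gives no value for r.

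| q | exempt | counted, r = 1% | counted, r = 2% |
|---|---|---|---|
| 10% | 0.973 | 0.965 | 0.956 |
| 20% | 0.816 | 0.798 | 0.779 |

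Now suppose exactly one of the first six patients has such an event and no other DLT, and none occurs among any added six. Classification changes the final outcome (expand or stop) in two cases. In the first, the other five have one DLT and the added six have two or more. In the second, the other five have two DLTs and the added six have at most one.

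- q = 10%: 0.328 × 0.114 + 0.073 × 0.886 = about 10%.
- q = 20%: 0.410 × 0.345 + 0.205 × 0.655 = about 28%.

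**6. Why r cannot be taken from the background data.** Section 1.2.5.3 describes intratumoral injection-site reactions as mostly Grade 1 or 2. In CMP-001-001 no Grade ≥3 event other than hypotension reached 5%, but that bounds each term separately and not pain and irritation together. In CMP-001-002, 2 of 18 patients had Grade ≥3 tumour pain. That is an all-cause figure from a part described as SC dosing, and only one tumour-pain SAE was judged treatment-related. None of these is a rate for injected lesions in the first two intratumoral doses.

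**The case against.** The strongest reply is that the text is clear. The exemptions are alternatives, pain at an injected tumour meets the flare definition, and no precedence rule is needed. Whether inflammation in a deliberately injected lesion should stop a cohort is a clinical choice, and the sponsor may have made it. Section 3.2.5 also has the sponsor monitoring DLTs across the cohorts with power to pause or discontinue enrolment, and Section 9.8 provides an internal safety review team and regular discussions with investigators.

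Much of this stands. A reader might infer that Section 3.3 leaves the matter open, so that the same event is equally a DLT or exempt. The text does not support that, because its literal result is exemption. Inconsistent calls would arise only if an assessor labelled the event an injection-site reaction, as Section 5.3.7.3.4 invites, and did not go on to apply the flare definition. That is plausible in practice, and sponsor oversight makes it less likely.

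Two things survive. Oversight does not alter the definition that the primary endpoint uses. And nothing in the protocol indicates that unlimited exemption at injected lesions was intended: both neighbouring rules, for local reactions and for Combination F cytokine-type events, stop at Grade 3 and 24 hours.

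**Conclusion.** The point holds as a minor one and is best labelled a cheap improvement. As written, attributable Grade ≥3 pain or irritation at a CMP-001-injected lesion is exempt from DLT at any grade and for any duration. That is out of line with the limits the protocol sets for local reactions generally and for other expected Combination F toxicities.

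Its size is unknown and probably small. The figures above rest on assumed event rates and independence, and show only how the rule responds. A reader might infer from them that expansion decisions are materially distorted. The protocol gives no event rate that would support this, and the only direct description of intratumoral injection-site reactions points to mostly low grades.

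**What to change.** Add one sentence to Section 3.3:

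> *For Combination F, pain, irritation or other reactions at a CMP-001-injected or peritumoral injection site are assessed under the local-reaction exception (or, for rash, the Grade 3 skin-toxicity exception); the tumour-flare exception applies only to non-injected tumour sites.*

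If the sponsor does want such reactions exempt, Section 3.3 should say so and state a grade and time limit.

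No new data or listings are needed. The cost is that some on-target inflammation at Grade ≥3 lasting more than 24 hours would count as a DLT, slightly lowering the chance that a cohort expands.

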Treatment-related TEAEs have been reported in 109 (96.5%) patients. The most commonly occurring treatment-related TEAEs for all grades include chills (79 patients; 69.9%); fever (pyrexia) (66 patients; 58.4%), nausea (53 patients; 46.9%), fatigue (50 patients; 44.2%), vomiting (34 patients; 30.1%), headache (32 patients; 28.3%), decreased appetite and injection site pain (24 patients; 21.2%, each event), and diarrhea (23 patients; 20.4%). The only Grade 3 or higher treatment-related TEAE occurring in 5% or more of patients is hypotension (9 patients; 8.0%).

Thirty-seven (32.7%) patients have experienced at least 1 SAE. Serious AEs reported in more than 1 patient include hypotension (7 patients; 6.2%), sepsis (3 patients; 2.7%), and fever (pyrexia), cytokine release syndrome, encephalopathy, hypoxia, and respiratory failure (2 patients; 1.8%, each event). Most SAEs are not considered related to study treatment, however, SAEs that are considered related to combination study treatment reported in more

than 1 patient include hypotension (6 patients; 5.3%) and cytokine release syndrome (2 patients; 1.8%).

Study CMP-001-002

Study CMP-001-002, is evaluating CMP-001 administered as a SC injection in Part 1 and as a SC and IT injection in Part 2 in combination with pembrolizumab in patients with advanced melanoma.

As of 31 October 2018, 18 patients have received at least 1 dose of CMP-001 by SC or IT injection in the Part 1 Dose Escalation Phase of the CMP-001-002 study. Patients received CMP-001 at starting doses of 5 mg (n=10) or 10 mg (n=8; note: 2 of these 8 patients enrolled in the 10 mg dosing cohort were initially dosed with 5 mg) in combination with pembrolizumab 200 mg Q3W. No patients have been enrolled in the Part 1 Dose Expansion Phase or Part 2.

In the Part 1 Dose Escalation Phase, all 18 (100%) patients have experienced at least 1 TEAE and 11 (61.1%) patients have experienced Grade 3 or higher TEAEs. The most commonly occurring TEAEs for all grades include fatigue (11 patients; 61.1%), nausea (8 patients; 44.4%), chills (6 patients; 33.3%), fever (pyrexia) (5 patients; 27.8%), and diarrhea, headache, and rash (4 patients; 22.2%, each event). Grade 3 or higher TEAEs of anemia and tumor pain have been reported in 2 (11.1%) patients each.

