Preliminary analysis of safety data appears to demonstrate an acute toxicity profile for all 3 studies that consists predominately of Grade 1 to Grade 2 AEs including fever (pyrexia), chills, nausea, vomiting, diarrhea, headache, rash, and hypotension resembling interferon-related toxicities as well as symptoms associated with cytokine release. The most common Grade 3 or higher TEAE is hypotension. These AEs typically present within 1 to 4 hours after the third CMP-001 dose and generally resolve within a few hours with standard supportive care and/or stress dose steroids.

Mild to moderate injection site reactions following IT injections, such as pain, itching, erythema, swelling, and induration have been reported. These injection site reactions were mostly grade 1 or 2 events.

Efficacy

Study CMP-001-001

Preliminary efficacy data across the Part 1 Dose Escalation and Part 1 Dose Expansion Phases show an objective response rate (ORR) in 18 of 113 melanoma patients of 15.9% and is comprised of 2 CRs and 16 PRs. The 95% CI is 9.7% to 24.0%. The ORR using the combination of RECIST/immune-related Response Evaluation Criteria in Solid Tumors (irRECIST) is 19.5% (22 of 113 patients; 95% CI = 12.6% to 28.0%). An additional 4 patients are included as responders based on the irRECIST assessment due to achieving a PR after initial progression. There are 30 (26.3%) patients with a RECIST best response of SD, 50 (44.2%) patients with a RECIST best response of PD, and 11 (9.7%) patients who discontinued prior to having a follow-up scan.

Of the 18 patients with RECIST responses, 8 patients have responses of at least 48 weeks in duration, with 1 of these patients having an ongoing response at Week 108 and another patient with an ongoing response at Week 84. Three patients have a response duration of 24 weeks, 2 patients have a response duration of 12 weeks, and 1 elderly patient discontinued treatment after the Week 12 tumor assessment scan. As of the data cutoff date, 8 of the 18 patients with RECIST responses remain on treatment and 10 patients are off treatment.

Study CMP-001-002

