Avelumab premedication: in order to mitigate infusion-related reactions, patients must be premedicated with an antihistamine and with paracetamol (acetaminophen) prior to the first four infusions of avelumab. Premedication should be administered for subsequent avelumab doses based upon clinical judgment and presence and severity of prior infusion reactions. In Combinations A, B, C, and D, when two or three investigational products are to be administered on the same day, premedication should be given prior to the first investigational

product administration. This may be modified based on local treatment standards and guidelines.

Premedication in Combination F:

To reduce the severity of symptoms associated with CMP-001 induced cytokines, prophylaxis is mandated prior to the initial two SC (C1D1 and C1D8) and four IT (C1D15, C1D22, C2D1, C2D8) doses.

The following premedication regimen is mandated in prevention of CMP-001 induced reactions unless clinically contraindicated:

- Fluids (ie, 1000 mL IV normal saline);
- NSAIDS (ie, 1000 mg acetaminophen and 50 mg indomethacin);
- Anti-emetics (ie, 8 mg Zofran orally [per os (PO)]).

It is also highly recommended to continue to administer additional fluids **immediately following** the CMP-001 injection, rather than waiting to initiate fluids when hypotension is detected.

If some of these premedications are administered prior to avelumab infusion, they may not need to be repeated before CMP-001 administration. If the drug administration visit is spread over two consecutive days, appropriate premedication should be administered on both days, according to the study drug being administered on each day. Premedication for subsequent CMP-001 doses (C2D15 onwards) is recommended and should be administered based upon clinical judgment and presence and severity of prior infusion reactions. The CMP-001 premedication requirements are summarized in [Table 20](#).

Stress Dose Steroids

Prophylaxis with stress dose steroids is recommended for patients who have experienced CMP-001-related Grade 3 CRS lasting ≤ 24 hours (ie, a minimum dose of corticosteroids of 25 mg prednisone or equivalent [eg, hydrocortisone, methylprednisolone, and dexamethasone]) for subsequent CMP-001 doses. The selection and dose of corticosteroid should be determined by the Investigator based on clinical parameters.

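### The CRS line in the Section 3.3 DLT definition has no working effect: short Grade 3 CRS that needs steroids is a DLT by the letter, against the protocol's own 24-hour boundary

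*Protocol*

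**What the plan says.** Section 3.3 grades severity by CTCAE v4.03. For attributable non-hematologic, non-laboratory events in the DLT window, it counts any Grade 3 or higher "toxicity, except for any of the following", and then lists the exceptions: brief fatigue, local reactions or headache; controlled nausea and vomiting; hypertension; diarrhea; skin toxicity; asymptomatic amylase or lipase changes; endocrinopathy; and tumor flare. The CRS line is printed directly after these: "Grade 4 CRS or Grade 3 CRS lasting >24 hours despite optimal treatment".

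A paragraph specific to Combination F follows. It says that events such as headache, fever, flu-like symptoms or hypotension, of Grade 3 or lower, that resolve to Grade 1 or lower "within 24 hours with standard supportive care will not be considered as DLTs".

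Section 5.3.5.2 deals with dosing after short Grade 3 CRS: "Prophylaxis with stress dose steroids is recommended for patients who have experienced CMP-001-related Grade 3 CRS lasting" 24 hours or less, for subsequent CMP-001 doses.

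Sections 3.2.5 and 9.2.3 give the Combination F rule. A cohort goes to Phase 2 with at most 1 DLT in 6. With 2 in 6 it adds six patients and goes on if the total is at most 3 in 12. It stops at 3 or more in 6, or 4 or more in 12.

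**The concern.** DLT is the Phase 1b primary endpoint, and a duration limit in its definition should separate events that count from events that do not. This one separates nothing. A patient with Grade 3 CRS that clears in a few hours on stress-dose steroids meets the general rule, meets no exception, and is a DLT. Yet the 24-hour limit in the CRS line, and the dosing guidance that uses the same boundary, both suggest that such an event was meant to be tolerable.

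Two careful readers can therefore count the same patient differently. In Combination F one extra DLT can move a cohort from 1/6 to 2/6 (six more patients before Phase 2), from 2/6 to 3/6 (stop), or from 3/12 to 4/12 (stop).

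**Working it through.** **Step 1: the text.** Take Grade 3 CRS lasting 24 hours or less, treated with stress-dose steroids.

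- General rule (Section 3.3): Grade 3, so a DLT unless excepted.
- Exception list: no item names CRS.
- CRS line as a DLT criterion: it names Grade 4 CRS and longer Grade 3 CRS, both already caught by the general rule. It adds nothing and exempts nothing.
- Combination F paragraph: it requires resolution to Grade 1 or lower within 24 hours with standard supportive care. Two places set steroids apart from that. Section 1.2.5.3 speaks of "standard supportive care and/or stress dose steroids", and Section 5.3.7.3.3 gives stress-dose steroids as the step for hypotension that has not responded to supportive care such as fluids. Read strictly, the paragraph does not reach this patient, nor one whose event falls only to Grade 2.

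The event is a DLT by the letter.

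**Step 2: can it fall in the window?** Section 1.2.5.3 says that CMP-001 events "typically present within 1 to 4 hours after the third CMP-001 dose". In Combination F the third dose is the first intratumoral one, on C1D15 (Table 20). The DLT window is "4 weeks including the first two weekly SC injections and the subsequent two weekly IT administrations" (Section 9.1.3), so it covers that dose.

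**Step 3: reproduce Table 29.** With true DLT rate p:

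- P(straight to Phase 2) = P(X ≤ 1 | 6, p)
- P(expand) = P(X ≤ 1 | 6, p) + P(X = 2 | 6, p) × P(Y ≤ 1 | 6, p)

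At p = 0.10: 0.8857 + 0.0984 × 0.8857 = 0.973 (Table 29: 0.97). At p = 0.20: 0.816 (0.82). At p = 0.30: 0.556 (0.56). The other six entries also reproduce. Table 29 is correct.

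**Step 4: effect of counting the event.** Let b be the rate of other DLTs (assumed) and c the rate of short Grade 3 CRS outside the exemption, taken as independent. Then p = 1 − (1 − b)(1 − c).

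The Protocol gives no value for c. Section 1.2.5.3 offers two proxies from study CMP-001-001, both for the whole study: related serious CRS, 2/113 = 1.8%, and related Grade 3 or higher hypotension, 9/113 = 8.0%.

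For b = 0.10 and c = 2/113: p = 1 − 0.90 × 0.9823 = 0.116. For b = 0.10 and c = 9/113: p = 1 − 0.90 × 0.9204 = 0.172.

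| Other DLTs (b) | P(expand), not counted | counted, c = 1.8% | counted, c = 8.0% |
|---|---|---|---|
| 5% | 0.997 | 0.992 | 0.947 |
| 10% | 0.973 | 0.958 | 0.875 |
| 20% | 0.816 | 0.783 | 0.656 |

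At b = 0.10, P(straight to Phase 2) goes from 0.886 to 0.853 or 0.725. Counting can only add DLTs, so the fall in P(expand) is the chance that a cohort's final decision differs: 0.015 or 0.097 at b = 0.10.

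**The case against.** The strongest reply is that a specific line governs a general one. On that view the CRS line alone decides CRS: Grade 4, or Grade 3 beyond 24 hours, is a DLT and anything shorter is not. The line has no other evident purpose, and Section 5.3.5.2 uses the same boundary. This is probably the intent, but Section 3.3 does not say so. Its closing paragraph lets Sponsor and Investigator define further events as DLTs; it does not provide for setting aside one that meets the criteria.

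It is also fair that the Combination F paragraph is open-ended and covers much of the ground. Short Grade 3 cytokine-type events that settle to Grade 1 or lower with standard supportive care are already exempt, so only the remainder is in dispute. Figure 22, the treatment algorithm, is not shown, so the point about steroids rests on Sections 1.2.5.3 and 5.3.7.3.3.

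Stronger readings that a reader might infer are not supported:

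- *That the line exempts the worst CRS*, because it is printed with the exceptions. The bullet nesting may be lost in the PDF text, and the point does not depend on it.
- *That the Protocol expects short Grade 3 CRS as the usual case.* Section 1.2.5.3 describes mainly Grade 1 to 2 events.
- *That the CRS grading scale is left open.* Section 3.3 names CTCAE v4.03; Table 23 belongs to the management section, and no text assigns it to DLT calls.

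**Conclusion.** The definition is wrong as written. It gives a result at odds with the 24-hour boundary that the Protocol uses in the line itself and in Section 5.3.5.2. It calls for a wording correction, between minor and should-fix.

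The effect is small at the CRS proxy and moderate only in the upper case. Neither proxy measures the uncovered event. The 1.8% is serious CRS of unstated grade and duration. The 8.0% would require every hypotension event to be CRS, short and outside the exemption. Both come from a study that gave CMP-001 intratumorally, mostly at 5 mg, whereas Combination F gives 10 mg with two subcutaneous priming doses and mandated premedication. The rates of other DLTs and their independence are assumptions.

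A reader might infer a risk of unsafe expansion. The text does not support that: literal counting adds DLTs, and the Sponsor may pause enrollment at any time (Section 3.2.5). The risk is inconsistent counting and an unintended delay or stop.

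**What to change.** In Section 3.3:

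1. Move the CRS line out of the exception list and state it as a stand-alone DLT criterion: CRS of Grade 4 or higher, or Grade 3 CRS lasting more than 24 hours despite optimal treatment.
2. Add an exception: Grade 3 CRS that resolves to Grade 1 or lower within 24 hours with optimal treatment, including stress-dose steroids.
3. Use the same treatment wording in the Combination F paragraph.

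Optionally, add a cross-reference saying whether CTCAE v4.03 or Table 23 grades CRS for DLT calls.

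The cost is one or two lines in a clarification letter or amendment. Sample size, decision rules and Table 29 do not change.
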